6.2 Patient Stratification

Participants will be stratified as having peripheral or central lung lesions and the randomization process will ensure equal numbers of participants with peripheral or central lung lesions on each arm of the study.

7. RADIATION THERAPY TREATMENT PLAN

Intensity modulated radiation therapy (IMRT) is the only acceptable form of treatment planning allowed for this protocol.

SBRT radiation treatment planning overview

For each participant, we will determine the tissue-specific radiation dose to vital body structures using SBRT planned treatments. SBRT treatments will be planned using normal tissue dose constraints according to national lung SBRT clinical trials (RTOG 0915 (peripheral tumors) and RTOG 0813 (central tumors)).

Prediction of lymphocyte depletion using our current simulation algorithm

Using the existing simulation algorithm, we will predict the *in vivo* lymphocyte depletion for each participant on both arms to test the robustness of the algorithm.

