SBRT is a technique that allows high doses of radiation to be delivered to highly-focused extra-cranial targets by utilizing respiratory motion correction and daily image guidance ¹². SBRT provides an ideal setting to study radiation's effect on lymphocyte counts and function, due to the smaller target volumes which allow for flexibility in treatment planning options regarding entry and exit dose. Additionally, since this treatment does not usually include concurrent chemotherapy, it allows one to specifically evaluate radiation effects. SBRT lung optimization to reduce dose to the great vessels, lung, and heart are currently focused on maximal dose delivered to a small volume of the great vessel walls, and to the heart to reduce radiation injury to the vessel wall and intrathoracic hemorrhage. In the current study, we will continue to maintain the critical dose constraints to the heart, lung, and great vessels in both study arms, but we will also further optimize plans in the study group to reduce radiation to the regional great vessels, lungs, and heart beyond what is currently optimized to reduce the integral dose to circulating blood/lymphocytes.

While recent studies show that decreased fractionation is inversely related to total lymphocyte count (TLC) after treatment⁴, there are currently no tools to predict the decrease in lymphocyte count that should be expected with different radiation treatment plans. There was no clinical data available until our recent retrospective research^{13,14} showed a correlation of dose to different organs in the thorax and lymphocyte depletion. We used this data to develop an algorithm that predicts the decrease in TLC after lung SBRT treatment and we will test this model prospectively in this study. Data from this study will be used to refine the algorithm to make it more clinically robust by including functional lymphocyte effects in addition to absolute lymphocyte count effects. Ultimately, the goal will be to use the algorithm during SBRT planning to guide radiation dose optimization via utilization of predicted immune normal tissue complication probabilities in addition to dose optimization of other regional organs-at-risk (OAR) including the heart, esophagus, spinal cord, tracheobronchial system, lungs, chest wall, and brachial plexus.

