3. OBJECTIVES

3.1 Primary Objectives

3.1.1 Performance of Algorithm to Predict Decrease in Lymphocyte Count Post-SBRT

Determine if the lymphodepletion predictive algorithm developed by UVA coupled with the existing optimization algorithm in radiation treatment planning software predicts the magnitude of lymphocyte depletion in a prospective cohort of patients treated with lung SBRT.

Hypothesis: We hypothesize that our predictive algorithm, which estimates risk of post-SBRT lymphopenia based upon estimation of radiation dose to blood vessels, can accurately predict change in lymphocyte count at 4 weeks following SBRT in a prospective cohort of lung SBRT patients.

Endpoint: After randomization and completion of treatment planning, the algorithm will predict the decrease in lymphocyte count for each participant (in Arms A and B) at 4 weeks after SBRT. The predicted decrease will be compared with the actual decrease in lymphocyte count observed.

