3.3.4 Optimization of Predictive Algorithm

Improve our existing simulation algorithm to predict the total lymphocyte loss for a given RT beam plan using the clinical trial data.

Endpoints: This model will take into account patient specific (i) total blood volume, (ii) initial lymphocyte count, (iii) tumor volume, (iv) the organs from the Thorax CT data set, and (v) time dependent dose map through each organ for a given delivery system. These data will be combined with general information from published literature such as (i) varying blood output to organs (ii) blood velocity for all organs (iii) random mixing of blood after each trip through the exposed dose area, with the remaining blood volume of the body.

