5. STATISTICAL CONSIDERATIONS

Study populations Any participant who initiates either standard or optimized SBRT will be considered evaluable for adverse events. Participants with observed changes in lymphocyte counts at any of the follow-up times will be considered evaluable for the analyses of changes in lymphocyte counts.

Randomization and stratification

[figure not shown]
Participants will be randomized to standard or optimized SBRT in a 1:1 ratio using randomly permuted blocks. Block sizes of 2 or 4 will be randomly chosen with equal probability. The randomization will be stratified by central or peripheral lung lesion (section 4.1.1)

Sample size and power The first aim is to compare the actual and predicted values from the simulations. We will calculate the empirical distribution function of the difference between predicted and actual, both in terms of lymphocyte counts and percent change from pretreatment counts. Current simulation is able to predict to 17% accuracy, with a standard deviation of 15%. The model will be considered an improvement if 80% of the predictions are within 10% of the actual counts or percent changes. With a sample of size 50 evaluable, the one-sample t-test has 95% power, with a one-sided significance level of 5%, for testing whether the mean percent difference is less than 17%, when the true mean is 10%.

The second aim is to compare standard versus optimized SBRT on the basis of the primary outcome, lymphocyte drop at 4 weeks. The sample size was chosen to have sufficient power for comparing the groups using a repeated measures model for comparing the groups. Estimates of effect sizes and variation were based on repeated measures models, with change points at 4 and 12 weeks, fit to retrospective data on lymphocyte drop within 24 weeks following standard SBRT. A spatial-power model was used for the covariance matrix of percentage changes from baseline in lymphocyte counts,

yielding an estimated standard deviation of 10.5 percentage points and a within-subjects correlation estimate of 0.40 for observations taken 1 week apart. The fitted model, overlaid on the individual patient profiles is displayed above.

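### Primary Aim 1 sets out to validate the existing algorithm, but its only decision rule and its powered test ask whether that algorithm beats its own stated 17% accuracy

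*Combined protocol and SAP*

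**What the plan says.** All references are to the combined protocol and SAP.

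- **Objective.** Section 3.1.1 hypothesises that the algorithm "can accurately predict change in lymphocyte count at 4 weeks following SBRT in a prospective cohort of lung SBRT patients". It gives no numerical threshold.
- **Algorithm under test.** Section 7, under the subheading "Prediction of lymphocyte depletion using our current simulation algorithm", is explicit: "Using the existing simulation algorithm, we will predict the" in vivo "depletion for each participant on both arms to test the robustness of the algorithm".
- **Its known performance.** Section 5, Sample size and power: "Current simulation is able to predict to 17% accuracy, with a standard deviation of 15" percent.
- **Decision rule.** The next sentence in Section 5: "The model will be considered an improvement if 80% of the predictions are within 10% of the actual counts or percent changes".
- **Powered test.** Section 5 then gives a one-sample t-test, one-sided 5%, 50 evaluable participants, with 95% power to show a mean percent difference below 17% when the true mean is 10%.
- **Analysis text.** The Analyses paragraph of Section 5 tabulates the empirical distribution of the differences and reports the proportion within 10%. It repeats neither the 80% cut-off nor the t-test.
- **Where improvement takes place.** The Introduction says "Data from this study will be used to refine the algorithm". Exploratory objective 3.3.4 is to "Improve our existing simulation algorithm to predict the total lymphocyte loss for a given RT beam plan using the clinical trial data".

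**The concern.** The objective and the algorithm run for it describe a validation: does a tool built on retrospective data hold up prospectively? The rule and the test describe superiority over that same tool's stated accuracy. The documents mention no change to the algorithm between the 17% estimate and the trial, and they name no locked version.

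This is a primary aim, so the wording decides what gets claimed. If the algorithm performs prospectively just as it is said to perform now, that is informative for 3.1.1. Yet the formal rule would almost certainly record it as not met, as it would for an algorithm that performed worse. No stated criterion would confirm that 17% holds.

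**Working it through.** **Inputs (Section 5).** n = 50; null mean 17; alternative mean 10; SD 15; one-sided alpha 5%; rule: at least 80% of 50, that is 40 or more, within 10.

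**1. Reproduce the stated power.** Standard error = 15/√50 = 2.121. Noncentrality = (17 − 10)/2.121 = 3.30 on 49 df. Power from the noncentral t is 94.6% (normal approximation 95.1%). The stated 95% is confirmed.

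**2. Same test at other true means.**

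| True mean error | Probability of rejecting |
|---|---|
| 10% | 94.6% |
| 12% | 75% |
| 13% | 58% |
| 15% | 24% |
| 17% (stated current accuracy) | 5% |

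The critical t is 1.677, so rejection needs an observed mean below 17 − 1.677 × 2.121 = 13.4%.

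**3. The 80% rule at the stated accuracy.** The documents do not give the shape of the errors, so four were assumed: errors signed and normal, or absolute errors following a half-normal, lognormal or gamma distribution. The half-normal has one parameter, so matching a mean of 17 fixes its SD at 12.8; the other three use SD 15. The pass probability is the binomial tail P(X ≥ 40 of 50).

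| Shape, mean 17 | Within 10 | P(40 or more of 50) |
|---|---|---|
| Signed normal | 28.4% | 5.8e-14 |
| Half-normal | 36.1% | 2.7e-10 |
| Lognormal | 37.5% | 9.6e-10 |
| Gamma | 40.3% | 1.2e-8 |

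**4. The 80% rule at the plan's own alternative.** The half-normal with mean 10 has SD 7.6.

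| Shape, mean 10 | Within 10 | P(40 or more of 50) |
|---|---|---|
| Signed normal | 40.9% | 1.9e-8 |
| Half-normal | 57.5% | 0.0007 |
| Gamma | 69.2% | 0.064 |
| Lognormal | 70.6% | 0.094 |

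So the scenario in which the t-test has 95% power gives the 80% rule at most about a 9% chance under these shapes. Even unbiased normal errors with SD 15 put only 49.5% within 10. Reaching 80% without bias needs an SD of 10/1.282 = 7.8. If the true within-10% rate is exactly 80%, the rule is met 58% of the time. Section 5 states no power for the rule.

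**5. What the sample can estimate.** The 95% CI half-width for the mean error is 2.010 × 2.121 = 4.3 points. For illustration, 40 of 50 within 10% has an exact 95% CI of 66% to 90%.

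**The case against.** Several counter-arguments carry weight.

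- **A reader might infer that the rule is meant for a model that will exist only after the trial.** The documents do not say so. Section 5 refers only to the model, and the threshold is absolute, so it can be applied to the existing algorithm. Meeting it would be strong prospective evidence.
- **A reader might also infer that the trial cannot give a meaningful answer on validity.** That goes too far. The Analyses paragraph tabulates the full distribution of predicted-minus-actual differences and the proportion within 10%. An algorithm with 17% error would look visibly different there from a useless one.
- **Setting 5% against 95% does not expose a power error.** The first is the type I error at the null, the second the power at an alternative that Section 5 states openly. Any superiority test behaves this way.
- **There is some reason to hope for smaller error here.** The exclusions in 4.1.2 and the follow-up rule in 8.1.3 remove participants on treatments that disturb lymphocyte counts, and the rationales in Appendix 3 link this to the algorithm's accuracy. That is a direction of effect, not a figure, and it does not establish 10%.
- **The pass probabilities cannot be derived from a mean and SD alone.** A two-point distribution with 80% of errors at 9.5 and 20% at 47 has mean 17 and SD 15 and meets the rule 58% of the time. That shape is extreme, but the probabilities must be read as ranges under assumptions.

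The trial is also a pilot with a largely descriptive analysis for this aim. What remains is the mismatch between the validation objective and the only rule and test offered for it.

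**Conclusion.** The concern holds as a mismatch between the objective and its decision rule. Section 5's rule and t-test measure superiority over the stated accuracy of the very algorithm being run, and the documents supply no figure supporting a 10% error for that version. At the stated 17% the t-test rejects 5% of the time, and under the assumed shapes the 80% rule is met with probability about 6e-14 to 1e-8. The rule also fits poorly with the plan's own alternative, where it is met with probability about 2e-8 to 0.09. Under these shapes it therefore cannot separate an algorithm that performs as claimed from one that performs worse.

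The ranges rest on the assumed error shapes and on reading both the 17% and the 10% on one percentage scale. The documents do not say whether 17% is a signed or absolute error, or whether the 10% limit is relative or in percentage points. The t-test results need only the stated mean and SD and the usual t approximation. The power figure is correct as conditioned, and prospective accuracy can still be estimated from this trial.

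**What to change.** In Section 5, with matching wording in 3.1.1:

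1. Make the primary Aim 1 result the prospective mean percent error of the existing algorithm with its 95% CI, compared with the stated 17%. State whether the error is signed or absolute.
2. Keep the proportion within 10% as a descriptive result with an exact CI, and drop 80% as a pass/fail threshold. State whether 10% is relative or in percentage points.
3. State that the 95% power applies only if the true mean error is 10%, and that rejection is 5% if it is still 17%.
4. Reserve the word improvement for the refined model in 3.3.4.
5. Name the algorithm version that generates the predictions. If an updated version is meant, give its retrospective accuracy and freeze it before the first 4-week count.

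This changes wording and reporting only; sample size and procedures stay as they are. The price is that the headline claim becomes validation instead of improvement, and the 95% figure is shown as conditional.

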7.1 Dose Specifications

7.1.1 PTV Dose Prescription

The tumor will be prescribed 50-60 Gy in 5 fractions to the planning target volume (PTV).

7.1.2 Normal Tissue Organs-At-Risk (OARs)

For participants in Arm B, plans will meet standard of care tissue dose constraints as described above. For participants in Arm A, plans will meet standard of care tissue dose constraints (described above) and additional planning constraints to reduce the dose to the great vessels, including the circulating blood within them, to as low as achievable while still meeting the other RTOG 0915 and RTOG 0813 dose constraints. These constraints will be reported in the radiation planning score card and treatment plan per standard of care institutional policy.

7.1.3 Great Vessels and Heart

The great vessels and heart will be contoured using mediastinal windowing on CT to correspond to the vascular wall and all muscular layers out to the fatty adventitia. The great vessels should be contoured starting at least 5 cm above the superior extent of the PTV and continuing on every CT slice to at least 5 cm below the inferior extent of the PTV.

7.1.4 Dose Fractionation

Participants on both Arm A and Arm B will receive 50-60 Gy in 5 fractions to the PTV. Treatments should be delivered within 5-10 business days (excluding the weekend(s) and holidays when the clinic is closed).

7.2 Technical Factors

Only photon (x-ray) beams produced by linear accelerators with photon energies of 4-10 MV will be allowed.

7.3 Localization, Simulation, and Immobilization

7.3.1 Patient Positioning

Patients will be positioned in a stable position using the **BodyFix** system (Medical Intelligence, Munich, Germany), with suction to reduce mobility, allowing accurate reproducibility of the target position from treatment to treatment.

Patient immobilization must be reliable enough to ensure that, in combination with the techniques used to inhibit target motion, the gross tumor volume (GTV) does not deviate beyond the confines of the planning target volume (PTV).

7.3.2 Inhibition of Effects of Internal Organ Motion

Special considerations will be made to account for the effect of internal organ motion (e.g., breathing) on target positioning and reproducibility. Accelerator beam gating with the respiratory cycle for tumors that move >8mm, and treating the FULL_ITV (internal target volume) for others will be utilized. All systems used to account for internal organ motion will be consistent with standard of care lung SBRT at UVA.

Internal organ inhibition maneuvers must be reliable enough to ensure that the GTV does not deviate beyond the confines of the PTV as defined in Section 7.4.

7.3.3 Localization

Isocenter or reference point port localization images should be obtained on the treatment unit immediately before treatment to ensure proper alignment of the geometric center (i.e., isocenter) of the simulated fields. All participants in both arms will follow the exact same pretreatment image-guided radiation therapy (IGRT) protocol. On the first day of the treatment, planar kV imaging orthogonal images will be acquired to align the bony anatomy to the planning CT bony anatomy. Secondly, a cone beam CT image will be acquired and aligned to the planning, time averaged CT image. They will be registered such that soft tissue registration for the lung tumor is applied. The deviations between bony anatomy registration and soft tissue registration should be ≤7mm. In case of deviations >7mm, an additional cone beam computed tomography (CBCT) will be acquired to verify the target localization. OAR contours from the planning data set, such as the great vessels, and lung positioning, will be verified daily prior to radiation delivery.

In case of gated treatment, following the above mentioned two pre-treatment imaging verifications, a gated anterior posterior/lateral (AP/Lat) image would be taken to verify the tumor location within the gated window. For all participant treatments in all machines, agreement between the treatment unit isocenter and imaging isocenter will be verified each day to be within 1mm.

7.4 Treatment Planning/Target Volumes

7.4.1 Image Acquisition

Computed tomography (CT) will be the image platform for targeting and treatment planning. Axial acquisitions with spacing = 3.0 mm should be utilized. 4-dimensional CT image-guided (4DCT) internal target volume (ITV) around the GTV will take tumor motion into consideration and will be the primary method of target volume definition. This target will also be the clinical target volume (CTV)].

The target lesion will be outlined by an appropriately trained physician, using a maximum intensity projections (MIP) image of 4DCT and designated to be the internal target volume (ITV). The target will generally be drawn using CT pulmonary windows.

The PTV will include the ITV plus an additional 0.5 cm margin uniformly applied to the ITV. Up to an 8mm margin may be applied in the craniocaudad direction per the treating radiation oncologist preference. The planning CT would be the time averaged CT image from the four dimensional CT.

7.4.2 Dosimetry

IMRT coplanar or non-coplanar beam arrangements will be custom designed for each case to deliver highly conformal prescription dose distributions. Non-opposing, non-coplanar beams are preferable. Typically, approximately 10 beams of radiation will be used with roughly equal weighting. For arc rotation techniques, partial arcs or full arcs could be utilized. In order to obtain acceptable coverage, field aperture size and shape should correspond nearly identically to the projection of the PTV along a beam's eye view (i.e., no additional "margin" for dose buildup at the edges of the blocks or multi leaf collimator (MLC) jaws beyond the PTV). Prescription lines covering the PTV will typically be the 60-90% line (where the maximum dose is 100%).

For purposes of dose planning and calculation of monitor units for actual treatment, this protocol will require tissue density heterogeneity corrections. Algorithm used for heterogeneity corrections must be credentialed by the RTOG.

For patients in Arm A, the beam energy would be 6 X –FFF (flattening filter free) to minimize overall treatment time, and for angles whether it is arcs, or step and shoot, IMRT should be carefully selected such that overall lymphocyte reduction is at the maximum dictated by the prediction algorithm. An example of a planning study is given in *Figure 5* below.

Example Treatment Plans of a Central Tumor:

Aorta integral dose went from 721.1 x $181.63 = 1.3 \times 10^5 \text{ cGy}$ cc to $322.2 \times 181.63 = 5 \times 10^4 \text{ cGy}$ cc superior vena cava (SVC) integral dose went from $1769.7 \times 19.16 = 3.4 \times 10^4 \text{ cGy}$ cc to $438.3 \times 19.16 = 8.4 \times 10^3 \text{ cGy}$ cc.

This resulted in a reduction to the total great vessel dose from 1.6x10⁵ cGy cc to 0.6x10⁵ cGy cc.

Figure 5: Axial slice of a pat*i*ent's lung SBRT sample plan. On the left is a RTOG 0813 followed plan (as used in Arm B). Note the dose through the great vessels, aorta (orange), and superior vena cava (blue), compared to the plan on the right (as used in Arm A), where additional constraints were imposed on the dose to the great vessels.

7.5 Radiation Treatment Plan Pre-treatment Quality Assurance

All institutional standard of care SBRT quality assurance measurements and calculations will be made and the plan must pass these quality assurance processes within institutional standards

of care and be approved by the treating medical physicist and radiation oncologist prior to treatment delivery.

7.6 Image Guided Treatment

During pre-treatment IGRT for each fraction, the image registration procedure should include the proximal great vessels and heart location in addition to the treated tumor. This information will be recorded in the treatment notes by the therapist.

7.7 Discontinuation/Withdrawal of Therapy

Participants may withdraw or be discontinued from the study at any time for any of the following reasons:

- Inter-current illness that prevents further treatment
- Subject decides to withdraw from the study
- Unacceptable adverse events(s)
- Requirement of medication listed in the exclusion criteria
- If the investigator feels it is no longer in the participant's interest to continue participation
- Death
- Participant does not comply with study procedures

The primary reason for discontinuation or withdrawal should be entered into OnCore. All participants that discontinue or withdraw from the study will continue to receive standard of care treatment. Participants removed from study treatment for unacceptable adverse events will be followed until resolution or stabilization of the adverse event. Participants who have withdrawn consent will not be followed for any reason.

A participant's participation is considered completed when the subject has received all study treatments and has completed all follow-up procedures (or other milestone to define a completed subject).

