With n=25 patients, measured at baseline and 4 and 24 weeks months post radiation, the F-test in the repeated measures model provides 80% power for comparing the mean lymphocyte depletion profile over the follow-up period between the groups. For the power calculation, we assumed that in the optimized dose participants. mean lymphocytes relative to baseline are equal to Δ + $(1-\Delta)\mu(t)$, where $\mu(t)$ is the mean estimated from historical controls at time t = 0, 4, or 24 weeks. With this, $\Delta = 0$ means no effect of the optimization; $\Delta = 1$ means no

lymphocyte depletion with optimized SBRT treatment. *Figure 3* displays the mean profile for Δ = 0.60, a profile for which n = 25 per group yields 80% power for the F-test, with a 2-sided significance level of 5%. For the specific comparison at 4 weeks, a contrast in the repeated measures model has more than 99% power for the assumed profile. We computed power for the comparing the entire trajectory, and not just at 4 weeks, because of the uncertainty in the point at which the maximum drop and the maximum difference between the groups will occur. To allow for 10% dropout, 55 patients will be enrolled in the study.

Analyses. For the first aim, which compares the actual and predicted lymphocyte counts, the empirical distribution function of the differences, both in terms of the lymphocyte count and the percentage change from baseline, will be tabulated. We will assess the proportion of cases in which the predicted values is within 10% of the actual value. In addition to computing the empirical distribution functions, exploratory analyses will assess patient characteristics associated with the magnitude of the deviation between predicted and actual values.

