7.8 Definition of Evaluable and Replacement of Study Participants

Participants that discontinue from the study prior to the 4-week post-SBRT blood draw will be considered unevaluable for the analyses of lymphocyte counts and will be replaced. These participants will be evaluable for the tabulation of adverse events.

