8.1.3 Concomitant Medications

For this protocol, a prescription medication is defined as a medication that can be prescribed only by a properly authorized/licensed clinician. Medications to be reported in the Case Report Form (CRF) are concomitant prescription medications, over-the-counter medications, and herbal supplements. Whenever possible, corticosteroids/immune modulators should be avoided, especially around the time of CBC or research blood draws, as they can affect the lymphocyte count. If a participant requires any medication listed in the exclusion criteria during or in the 6 months following SBRT, he or she will no longer be followed for the study and no additional blood will be drawn for research purposes. If this occurs within the 4 weeks following SBRT, the patient will be replaced. These medications have been shown to affect the way white blood cells respond to radiation. There are no other prohibited medications related to study participation. Medications should be collected from 28 calendar days before registration through 6 months following SBRT.

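### Section 7.7 does not separate stopping SBRT from leaving the study, so with 7.8 the 4-week arm comparison can be selected on post-randomisation events

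*Combined protocol and SAP*

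**What the plan says.** Section 7.7 is headed as discontinuation or withdrawal of therapy, but its list opens with "Participants may withdraw or be discontinued from the study at any time for any of the following reasons". The reasons include intercurrent illness that rules out further treatment, unacceptable adverse events, need for an excluded medication, investigator judgement and non-compliance. For toxicity it adds: "Participants removed from study treatment for unacceptable adverse events will be followed until resolution or stabilization of the adverse event". Participants who withdraw consent are not followed at all.

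Section 7.8 gives the consequence for analysis: "Participants that discontinue from the study prior to the 4-week post-SBRT blood draw will be considered unevaluable for the analyses of lymphocyte counts". They are replaced, and what remains of them is this: "These participants will be evaluable for the tabulation of adverse events".

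Three other places bear on the point:

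- Section 5 defines the lymphocyte population more widely: "Participants with observed changes in lymphocyte counts at any of the follow-up times will be considered evaluable for the analyses of changes in lymphocyte counts". It states that the second aim is to "compare standard versus optimized SBRT on the basis of the primary outcome, lymphocyte drop at 4 weeks", and describes no missing-data or sensitivity analysis for those removed.
- Section 8.1.3 says that if an excluded medication is needed during SBRT or in the 6 months after it, "he or she will no longer be followed for the study and no additional blood will be drawn for research purposes". If this falls within 4 weeks of SBRT, the patient is replaced.
- The Section 9 calendar already schedules a CBC at 4 weeks and at 6 to 9 months, and survival checks by phone or record review.

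**The concern.** Stopping the intervention and leaving the trial are different events. A participant who stops SBRT early but still consents can give a 4-week CBC. Section 7.7 defines no path for that person: the stated follow-up after toxicity is tied to the event and not to the CBC schedule, and no section asks for the 4-week count after treatment stops.

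The 4-week drop is the primary outcome of the arm comparison. If those who tolerate treatment worst leave before the draw, the comparison is among those who stayed. Section 6.1 says treating clinicians know the arm, and one listed reason is investigator judgement, so leaving can depend on both arm and condition. Replacing these participants restores 25 per arm without restoring the balance that randomisation gave. Section 5's wider definition does not help at 4 weeks, because it cannot supply a count that was never drawn.

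**Working it through.** **Reading the sections together**

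1. Section 7.7 permits discontinuation from the study for reasons that arise from treatment or illness.
2. Section 7.8 makes anyone discontinued before the 4-week draw unevaluable for lymphocyte counts and replaces them.
3. No section keeps the scheduled CBC after SBRT stops.
4. So for such a participant the primary count need not be drawn, and would not be analysed under 7.8.

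**The plan's own allowance.** Section 5 states: "To allow for 10% dropout, 55 patients will be enrolled in the study". This reproduces: 50 × 1.10 = 55 (dividing instead, 50/0.90 = 55.6, so 56). It is an all-cause figure; no rate is given by reason or arm.

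**Standard error.** Section 5 gives an SD of 10.5 percentage points and 25 per group. For a simple two-group comparison, SE = 10.5 × √(2/25) = 2.97 points.

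**Size of the bias.** Let fA and fB be the fractions removed before the draw, and g the extra drop those participants would have shown compared with those kept.

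- Mean drop in a whole arm = mean in those kept + f × g.
- Observed difference (B minus A) = true difference − (fB − fA) × g.

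The values of f and g below are assumptions.

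| fA | fB | g (points) | Shift in B − A | Shift / SE |
|---|---|---|---|---|
| equal | equal | any, same in both arms | 0 | 0 |
| 5% | 10% | 15 | −0.05 × 15 = −0.75 | 0.75/2.97 = 0.25 |
| 10% | 20% | 20 | −0.10 × 20 = −2.0 | 2.0/2.97 = 0.67 |

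In both non-zero rows Arm B is assumed to lose more participants, so the Arm A benefit is understated. If Arm A lost more, the sign would reverse. The first scenario averages 7.5% removed, inside the 10% allowance; the second averages 15%, above it.

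**Against the planned effect.** Section 5 claims more than 99% power for the 4-week contrast. With SE 2.97 and two-sided 5%, 99% power needs (1.96 + 2.326) × 2.97 = 12.7 points. The historical mean curve is in a figure that is not shown, so this cannot be checked further. Relative to 12.7 points, the shifts are 0.75/12.7 = 6% and 2.0/12.7 = 16%.

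**The case against.** The strongest reply is that this is ambiguous wording and not a rule that removes people. Section 7.7 says participants may be discontinued. It also uses two terms, leaving the study and removal from study treatment, and only the first triggers 7.8. Where the protocol means to end follow-up or draws it says so: for withdrawn consent in 7.7 and for excluded medication in 8.1.3. This stands, so the missing count is an inference from 7.7 read with 7.8. It does not close the gap, because nothing says which term applies to a consenting participant who stops early.

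Four stronger readings are tempting and not supported:

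- That the 4-week count is never drawn after early stopping. No section says this.
- That anyone who falls ill before the 4-week visit is lost. The illness criterion concerns further treatment, and 7.1.4 has the 5 fractions delivered within 5 to 10 business days, so it covers only that short course.
- That 15/65 = 23% will be removed. The Synopsis figure of 65 is an enrolment ceiling, and Appendix 3 says it also covers screen failures.
- That power is lost. Replacement under 7.8 protects the numbers; the issue is bias.

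It is also fair that unequal removal is speculative. Both arms share a prescription range and the same organ constraints, and 3.2.1 hypothesises similar adverse-event profiles apart from lymphocyte decreases. Finally, retaining incomplete courses affects the first aim, where the algorithm predicts from the treatment plan. The fix has to deal with that.

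**Conclusion.** The point holds as a gap in 7.7 and 7.8. As written, the plan allows the primary randomised comparison to exclude participants on post-randomisation events decided with knowledge of the arm, and provides no analysis that would show the effect.

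The size is probably modest: zero under equal removal rates and equal excess drops, 0.75 points (0.25 SE) under the assumed scenario that fits the 10% allowance, and 2.0 points (0.67 SE) under one that exceeds it. The direction depends on which arm loses more. Few participants may stop during so short a course, and confidence in any particular size is low because the documents give no rates by reason or arm. The change is worth making because it is cheap and a 4-week count that is not drawn cannot be recovered later.

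**What to change.** - State in 7.7 and 7.8 that stopping SBRT does not by itself end study participation. Unless consent is withdrawn, the participant keeps the already scheduled 4-week and 6-to-9-month CBCs and survival checks.
- For the second aim, analyse these participants in their assigned arm, with a sensitivity analysis limited to those who completed SBRT.
- For the first aim, report results in those who completed the planned course, with all participants as the sensitivity analysis.
- Reconcile the new wording with 8.1.3, which ends follow-up and research blood when an excluded medication is needed, and with the evaluable definition in Section 5.
- Make no change to when treatment is stopped.

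The cost is a short amendment and a few CBCs that are already on the calendar. The downside is slight dilution of the arm contrast by incomplete courses, which the completers analysis would show. Counts lost to death or withdrawn consent stay missing.
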